#### End Date

- If end date is completely missing, it will be assumed that the AE is still ongoing and will not be imputed.
- If the end date is missing the day, the last of the month will be used (i.e. UNK-JAN-2022 becomes 31-JAN-2022)
- If the end date is missing the month, the subsequent month after the start date will be used.
- If the end date is missing the year, the year of first treatment will be used, provided the imputed date is after the start date; otherwise, the subsequent year after start date will be used.

Adverse events with a completely missing start date will be considered treatment-emergent unless the event has a stop date prior to the date of the first dose of study drug. All AEs will be listed by treatment and subject. Dates will be presented as collected in the listings.

In addition, a summary of all AEs will be provided, which will include (but is not limited to):

- number of subjects with at least one AE and number of events (in total as well as serious AEs),
- number of subjects with at least one related AE and number of events (in total as well as serious AEs),
- number of subjects with at least one unrelated AE and number of events (in total as well as serious AEs),

GALDERMA EST. 1981	Title 05DF2007 Statistical Analysis Plan (SAP)	CC I [REDACTED]
-----------------------	--	--------------------

- number of subjects who did not have an AE.

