## 2. STUDY OBJECTIVES AND ENDPOINTS

### 2.1 Objectives and Endpoints

#### 2.1.1 Safety Objective and Endpoints

The safety objective of the study is to evaluate the safety of *Restylane Kysse* for lip augmentation in Chinese subjects via assessment of:

- AEs at all study visits.

CCI

CCI

Safety endpoints include:

- Incidence, intensity, duration, and onset of related AEs collected during the entirety of the study.

CCI

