### 9.4 Data Transformations

Responder rate (%) regarding MLFS will be calculated as (number of subjects (or upper/lower lips) with at least one grade improvement from baseline/number of subjects reporting at the specified visit) \*100.

Responder rate (%) regarding WAS will be calculated as (number of subjects (or upper/lower lips) with at least one grade improvement from baseline/number of subjects reporting at the specified visit)\*100.

Responder rate (%) regarding GAIS will be calculated as (number of subjects being at least improved/number of subjects reporting at the specified visit) \*100.

The outcome of the questionnaires regarding FACE-Q will be summarized and transformed to a Rasch score (0-100).

Time to onset of an AE will be derived as the start date minus the date of most recent treatment. If the start date is missing, it will be assumed that the AE started on the day of most recent treatment.

Duration of an AE will be derived as the stop date minus the start date + 1. If the start date is missing, it will be assumed that the AE started on the day of most recent treatment. Missing stop date will not be imputed and therefore no duration will be calculated in these cases. Instead, the number of AEs that were ongoing at the end of the study will be given.

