## 2 Statistical Methods

### 2.1 General Methods

Any change made to the finalized SAP before database lock will result in an SAP amendment. Otherwise, changes will be documented in the Clinical Study Report (CSR). However, if additional supportive or exploratory analyses are requested after SAP approval, this will not require amendment of the SAP, but these additional analyses will be described in the CSR.

Some of the analyses detailed here may be more explicit or in some respects different from those stated in the protocol. In case of differences, this SAP supersedes the statistical sections in the protocol.

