#### 2.5.2 Adverse Events (AEs)

All AEs will be coded according to MedDRA and summarized by System Organ Class (SOC), and Preferred Term (PT), including number of subjects with at least one event, associated percentage, and number of events.

For subject counts, a subject will only be counted once per SOC and once per PT in cases where multiple events are reported for a subject within SOC or PT. For event counts, subjects with multiple events in a category will be counted for each event.

The number of subjects with AEs related to study product or study product injection procedure, as well as the number of events, will be presented by SOC, PT, and maximum intensity. Action taken for related AEs will also be summarized by SOC and PT using number of events. Serious AEs will be listed. AEs related to study product or injection procedure with late onset (> 21 days after most recent treatment session) will be listed.

AEs unrelated to study product or injection procedure will be summarized by SOC, PT, and maximum intensity.

For AEs related to study product or study product injection procedure, the number of days to onset and the duration of event will be summarized by SOC and PT using mean, standard deviation, median, minimum, and maximum. Days to onset of an AE will be derived as the start date minus the date of most recent treatment session. Duration of an AE will be derived as the stop date minus the start date + 1.

For the purpose of deriving days to onset and duration, the following date imputation rules will be used.

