### 2.8 Changes in the Analysis Planned in the Protocol

There have been no substantial changes from the statistical methods described in the protocol.

GALDERMA ESI: (RE)	<small>Title</small> 05DF2007 Statistical Analysis Plan (SAP)	CC I [REDACTED]
-----------------------	---	--------------------

2023-10-06 23:03

Effective date:

*Effective*

Version: 1.0

Effective date: 2023-10-06 23:03

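### Duration of related AEs is summarised only for events with an end date, and the visible SAP text does not restate the protocol's count of events still ongoing

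*SAP*

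**What the plan says.** Protocol 2.1.1 names the safety endpoint: "Incidence, intensity, duration, and onset of related AEs collected during the entirety of the study".

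SAP 2.5.2 gives the derivation, "Duration of an AE will be derived as the stop date minus the start date + 1", and the summary for related events: "the duration of event will be summarized by SOC and PT using mean, standard deviation, median, minimum, and maximum". Its End Date rules impute partial end dates. For an end date that is missing altogether the rule is: "If end date is completely missing, it will be assumed that the AE is still ongoing and will not be imputed".

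Protocol 9.4 also leaves a missing stop date unimputed and calculates no duration, but it then adds: "Instead, the number of AEs that were ongoing at the end of the study will be given".

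On precedence, SAP 2.1 says: "In case of differences, this SAP supersedes the statistical sections in the protocol". SAP 2.8 says: "There have been no substantial changes from the statistical methods described in the protocol".

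**The concern.** Having no end date is related to length. An event still open when the subject leaves the study has usually lasted longer than those that closed, so leaving it out of the duration statistics is not a neutral omission. A reader who sees a mean and maximum by preferred term cannot tell from that table how many events were left out.

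The protocol's ongoing count deals with this: it tells the reader how incomplete the duration figures are. A programmer working only from the visible SAP text has no instruction to produce it.

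Protocol 1.4 says the study is meant to support a future marketing application, and there are only about 50 subjects. A single open event can therefore matter to the mean and maximum for a given preferred term.

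**Working it through.** **1. The rules side by side**

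| Item | Protocol 9.4 | SAP 2.5.2 |
|---|---|---|
| Duration | stop − start + 1 | same |
| No stop date | not imputed, no duration | taken as ongoing, not imputed, so no duration |
| Partial end date | not addressed | imputed (a missing day becomes the last of the month) |
| Count of ongoing AEs | to be given | not in the visible text |

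The exclusion is therefore the protocol's own rule. Only the companion count differs, and there the SAP is silent. The SAP's AE overview list has no such item, but it is expressly open-ended.

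**2. Direction**

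The maximum over ended events cannot exceed the maximum over all events. The mean over ended events is too low whenever the open events last longer, on average, than the ended ones. That is the expected case, though not a certainty for an event that began shortly before exit.

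**3. Size, first illustration (assumed)**

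Neither document gives a duration figure or a number of open events, so there is no figure of the plan to reproduce. Assume 40 related events, of which *k* are open at Week 48, with the ended ones averaging 10 days. Week 48 is 48 × 7 = 336 days. An event that began on the day of last injection and is still open has lasted at least 336 − 0 + 1 = 337 days.

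Mean including open events ≥ [(40 − k) × 10 + k × 337] / 40

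| k open | Mean, ended events only | Mean, open events at their minimum |
|---|---|---|
| 0 | 10 | 10 |
| 1 | 10 | (390 + 337)/40 = 18.2 |
| 2 | 10 | (380 + 674)/40 = 26.4 |
| 4 | 10 | (360 + 1348)/40 = 42.7 |
| 8 | 10 | (320 + 2696)/40 = 75.4 |

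The median moves much less. If a fraction *f* is open and ranked longest, the overall median is the 0.5/(1 − f) quantile of the ended durations. With exponential ended durations of mean 10 it is −10 ln[1 − 0.5/(1 − f)]. That gives 6.9 days at f = 0, 7.2 at 2.5%, 7.5 at 5%, 8.1 at 10% and 9.8 at 20%.

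**4. Size, second illustration (assumed)**

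Let durations be exponential with true mean *m*, with onset on the day of last injection and stop dates known only up to day *T*. Then the fraction open is e^(−T/m), and the mean of ended events is [m − (T + m)e^(−T/m)] / [1 − e^(−T/m)]. Two cut-offs are used. T = 336 is Week 48. T = 420 adds the three months of post-study follow-up in Protocol 7.1.4, at the synopsis's four weeks per month (336 + 84).

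| True mean (days) | Open at 336 | Ended-only mean, T = 336 | Ended-only mean, T = 420 |
|---|---|---|---|
| 7, 14 or 30 | about 0% | unchanged | unchanged |
| 90 | 2.4% | 81.8 | 86.0 |
| 180 | 15.5% | 118.5 | 134.9 |
| 365 | 39.8% | 142.6 | 170.6 |

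Worked line, m = 90, T = 336: e^(−336/90) = 0.0239, and (90 − 426 × 0.0239)/(1 − 0.0239) = 81.8.

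When many events are open the median suffers too. At m = 180 the ended-only median is 98.9 days against a true 124.8 (T = 336).

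**The case against.** A reader might infer that the SAP has removed the protocol's count. The documents do not show that. The count sits in the protocol's Data Transformations section, whose SAP counterpart, 2.1.3, is redacted. The SAP's AE overview is not limited to the items it lists, and table formats are in a companion document that is not available. The SAP overrides the protocol only where the two differ, and silence is not plainly a difference.

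A reader might also infer that long reactions disappear from the safety report, or that the table holds only short events. Neither follows. A related event that lasted 300 days and ended is counted in full. An open event stays in the related-AE tables by SOC, PT and maximum intensity, and in the full AE listing with dates as collected. If it began more than 21 days after the most recent treatment session, it is also in the late-onset listing.

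The bias may be nil. Protocol 1.5 says injection site reactions generally resolve within one to two weeks. Its remark about swelling and mass weeks to months after injection concerns when they were reported, not how long they lasted. Month-end imputation of partial end dates, and baseline imputation of a missing start date, can lengthen some durations.

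All of this stands, and it limits the point to a reporting gap of unknown size. It does not close the gap. The SAP places the duration formula and date rules in 2.5.2, which is readable, and the count is not there. The statement of no substantial change is weak reassurance about a neighbouring rule. Protocol 9.4 sets a missing AE start date to the most recent treatment and the SAP sets it to baseline, yet SAP 2.8 still reports no substantial change. Imputing partial dates does not bring back events with no end date.

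**Conclusion.** The point holds as a gap in reporting. Following the visible SAP text, duration of related AEs is summarised only for events with a full or partial end date, and nothing in that text tells the analyst to show how many were left out. If related events are open, the mean and maximum are likely to be too low, while the median shifts little unless the open share is large.

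The size rests wholly on assumptions. There is essentially no bias if true durations average 7 to 30 days. In the 40-event example, one open event takes the mean from 10 to at least 18.2 days and four take it to at least 42.7. The example assumes onset at last injection; a later onset gives a smaller minimum.

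One further point is unsettled. Protocol 7.1.4 follows related events after exit until they resolve, are judged chronic or stable, contact is lost or three months pass. Neither document says whether stop dates from the AE Follow-up form enter the duration analysis. An event judged chronic may never receive a stop date.

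**What to change.** In SAP 2.5.2:

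- Show the number of related AEs without an end date, by SOC and PT, beside the duration statistics.
- Label those statistics *events with an end date only*.
- For each ongoing event, give the minimum known duration, from start date to last contact, flagged as ongoing.
- State whether stop dates from the post-study AE Follow-up form are used.

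A censored (Kaplan-Meier) median is optional; by preferred term it would often rest on very few events.

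No new data are needed. Protocol 7.1.1.2 already records outcome in the eCRF, including ongoing, chronic or stable, and not recovered at study end. That field also helps separate open events from those whose stop date was simply not obtained. The cost is a short SAP wording change and one extra column, and reported durations may look less favourable.

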### 1.5 Risks and Benefits

As the lip appearance is an essential feature in determining the attractiveness of a face, and thus, plays a key role in human social interactions. The primary potential benefit of the study product is a perceived improvement in the visual appearance of lip fullness.

For subjects in the US, another potential benefit is the correction of the upper perioral rhytids, philtral columns and oral commissures.

Injection site reactions (e.g. swelling, erythema, tenderness, pain, bruising, itching, lumps/ bumps, and discoloration) experienced with HA fillers have been observed as consisting mainly of short-term minor or moderate symptoms starting early after treatment that generally resolve spontaneously within one to two weeks after injection. According to published literature, the most common complications related to HA injections in the lips include these injection site reactions.

The most common adverse events (AE) reported in both post-marketing surveillance data and clinical trial data for the *Restylane*® family of products (utilizing the XpresHAn/OBT Technology) injected in the lips are swelling, mass/induration, papules/nodules, pain/tenderness, and bruising/bleeding.

Although most AEs occur within days to weeks following the implant procedure, some AEs, such as swelling and mass, have been reported several weeks to months after the injection. Inflammation, infection, and damage to body structures such as nerves or blood vessels at the injection site, have also been reported. Rare but serious AEs associated with the intravascular injection of soft tissue fillers in the face have been reported and include temporary or permanent vision impairment, blindness, cerebral ischemia or cerebral hemorrhage, leading to stroke, skin necrosis, and damage to underlying facial structures.

Additional information about reported AEs and anticipated risks are included in the product-specific IFU.

To mitigate these risks, only study investigators qualified by education and experience, and who are skilled in the use of dermal fillers from their clinical practice and involvement in clinical research, and with a firm knowledge of the vascular anatomy and understanding of the depth and plane of injection as well as knowledge of the signs and symptoms and management of potential complications will be chosen in order to assure proper device implantation and management of study risk.

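### The SAP's rules for partial adverse-event end dates make some short events about a month or a year too long

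*SAP*

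**What the plan says.** Protocol 2.1.1 gives the safety endpoint as "Incidence, intensity, duration, and onset of related AEs collected during the entirety of the study". SAP 2.5.2 supplies the formula: "Duration of an AE will be derived as the stop date minus the start date + 1". For related events, duration is summarised by system organ class and preferred term (PT) with mean, SD, median, minimum and maximum.

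The End Date rules in the same section cover four patterns:

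- Wholly missing: "If end date is completely missing, it will be assumed that the AE is still ongoing and will not be imputed".
- Day missing: the last day of the recorded month is taken.
- Month missing: "If the end date is missing the month, the subsequent month after the start date will be used". No condition is attached.
- Year missing: the first choice is the calendar year of first treatment. A condition and a fallback are attached to it: "provided the imputed date is after the start date; otherwise, the subsequent year after start date will be used".

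The Start Date rules just above accept an imputed date that falls *on or after* first treatment; the end-year rule requires *after*. Protocol 9.4 computes no duration when the stop date is missing and has no rule for a partial one. SAP 2.1 gives the SAP precedence over the protocol's statistical sections, so nothing elsewhere repairs these rules.

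**The concern.** Protocol 1.5 expects injection-site reactions to "generally resolve spontaneously within one to two weeks after injection". A month rule that can never place an end in the month of onset, and a year rule that can skip the year of onset, both run against that expectation. The year rule also rejects an end on the start day, although the formula's + 1 exists so that such an event counts as one day.

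The results go into descriptive safety tables for about 50 subjects, in a study meant to support a marketing application in China (Protocol 1.4). Many PTs will hold only a few events, so one wrong value could show a brief swelling as lasting a year. The start date, which would prevent most of this, is already collected.

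**Working it through.** **Inputs.** The formula and the partial-date rules come from SAP 2.5.2, read literally. *Subsequent year after start date* is read as start year + 1. All dates below are illustrative.

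**1. The SAP's own example.** An unknown day in January 2022 becomes 31 January 2022. This is reproduced.

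**2. Year missing** (stop − start + 1)

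| First treatment | Start | Recorded end | Imputed end | Duration | True |
|---|---|---|---|---|---|
| 15 May 2023 | 10 Jan 2024 | 15 Jan, year unknown | 15 Jan 2025 | 371 + 1 = 372 | 6 |
| 11 Dec 2023 | 10 Jan 2024 | 14 Jan, year unknown | 14 Jan 2025 | 370 + 1 = 371 | 5 |
| 15 May 2023 | 15 May 2023 | 15 May, year unknown | 15 May 2024 | 366 + 1 = 367 | 1 |

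In the first two rows the 2023 candidate precedes the start, and 2024 is never tried. In the third row the candidate equals the start and so fails the strict test; without an intervening 29 February the result is 366. A 5-day event that starts and ends in the first-treatment year is imputed correctly.

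**3. Month missing**

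| Start | Recorded end | Recorded year kept | Month simply follows onset | True |
|---|---|---|---|---|
| 16 May 2023 | day 20, 2023 | 20 Jun 2023: 36 | same | 5 |
| 5 Dec 2023 | day 12, 2023 | 12 Jan 2023: −326 | 12 Jan 2024: 39 | 8 |
| 20 Nov 2023 | day 3, 2024 | 3 Dec 2024: 380 | 3 Dec 2023: 14 | 45 if it ended in January |
| 28 Jan 2023 | day 30, 2023 | 30 Feb: no such date | same | 3 |

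The SAP does not say which of the two readings applies.

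**4. How often, given that the part is missing.** With start days spread evenly over a month of 30.4 days, the share of D-day events ending in their start month is (30.4 − (D − 1))/30.4. That is 24.4/30.4 = 80% for 7 days and 17.4/30.4 = 57% for 14 days.

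I also enumerated every first-treatment date in 2023, with onset spread evenly over a window:

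- Year missing, 5-day event: about a year too long in 1.8% of cases (onset 0–13 days after first treatment), 5.6% (0–41 days, which reaches two weeks past a week-4 touch-up) and 49.6% (0–364 days).
- Year missing, one-day event: essentially 100%.
- Month missing, 5-day event: 28 or more extra days in about 78%, an impossible date in about 2%, and a negative duration in about 7% if the recorded year is kept.
- Day missing: about 15 extra days on average, at most 30.

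**5. Effect on a PT summary.** Nine 6-day events and one of 372 days: (9 × 6 + 372)/10 = 42.6 days, median 6, maximum 372. One 371-day value among 5-day events gives (19 × 5 + 371)/20 = 23.3 with 20 events and (49 × 5 + 371)/50 = 12.3 with 50.

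**The case against.** The damaging patterns should be rare. They need a stop date with day and month but no year, or day and year but no month. Stop date is a required AE item (Protocol 7.1.1.2), subjects are asked about AEs at every visit, eCRF entries are checked for incomplete or inconsistent data and queried (Protocol 10.4.1), and SAP programs are independently validated (SAP 2.1.1). A missing year can usually be recovered from the visit at which the event was recorded. This stands as an argument about frequency. It does not make the rules right.

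Safety analysis is descriptive, the median is robust, and listings show dates as collected. This also stands, but it lets a reader trace a bad value without correcting the table. Diary events are summarised as days with the event (SAP 2.5.3), and these rules are not stated to apply to them.

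Erring long may be called conservative for safety. An added year, or a negative value, is hard to defend on that ground. The day-missing rule also errs long, but there the true value cannot be recovered from the start date.

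Three stronger readings are tempting and not supported:

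- *About half of events are exposed to the year error.* With first treatments spread over a year, 336/(2 × 365) = 46% of a 48-week follow-up lies in the later calendar year, or 50% for 52 weeks. That weights follow-up time. Protocol 1.5 says reactions mostly start early, which points to the 1.8% and 5.6% figures, and those apply only to records already missing the year.
- *Negative durations will occur.* They need a December onset and the recorded year kept. If the year rolls forward, the error is an extra month.
- *The duration endpoint as a whole is corrupted.* The documents give no count of partial end dates.

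**Conclusion.** The end-date rules are wrong as written, with a probably low-frequency effect on a descriptive safety endpoint. Three faults follow from the text:

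1. With the year missing, a short event that starts in a later calendar year than first treatment gains about a year. This rests on reading the fallback as start year + 1.
2. With the year missing, a one-day event becomes 366 or 367 days, because the test is *after*.
3. With the month missing, no event can end in its start month, so a short event usually gains about a month. December onsets are undefined and impossible dates can arise.

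The mean, SD, minimum and maximum in small PTs are exposed; the median is not. The frequency shares assume first treatments spread evenly over a year and hold only among records with the relevant part missing. How many such records there will be is unknown.

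**What to change.** Amend the End Date rules before database lock, as SAP 2.1 allows:

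- Keep every recorded date part.
- Year missing: use the start year if that puts the end on or after the start, otherwise the next year.
- Month missing: use the start month if it agrees with the recorded year and puts the end on or after the start, otherwise the first later month that agrees with the recorded year.
- Recorded day does not exist in the imputed month: use that month's last day. This is the one exception to keeping recorded parts.
- Day missing: last day of the month, as now.
- Require end on or after start in every case.
- Cap imputed end dates at the last AE contact, including the post-study follow-up in Protocol 7.1.4, without overriding a recorded part. A cap at the last scheduled visit would be too early for related events followed after exit.
- Flag imputed durations in the listing.

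Under these rules the year-missing examples return 6, 5 and 1 days and the month-missing examples 5, 8, 45 and 3.

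The earliest compatible date can understate a long event, so also report the duration summary without imputed end dates. This also shows how much the day-missing rule contributes.

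The cost is a few lines of SAP text and program and one repeated table. Neither the protocol nor the eCRF changes.
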